Empowering Anxious Parents to Manage Child Avoidance Behaviors: A Randomized Trial of a Single-Session Intervention Targeting Parent Accommodation (Project BRAVE)

Hypotheses, Aims, and Analytic Plan
August 31, 2020

Study Timeline

Recruitment is projected to begin in July 2020 and extend through approximately June 2021.

NOTE: This analytic plan was developed prior to the study's lead authors ([name], [name]) downloading, seeing, or using any of the data collected as part of this trial. Similarly, other exploratory analysis will be pre-registered at a later date under the same conditions.

Study Aims and Hypotheses

The primary goals of the study will be as follows:

1. Examine the SSI's (ORR+Project BRAVE) direct effects on parental accommodation, relative to an information-only control (ORR+delayed SSI) at two weeks follow-up.
2. To assess whether parents' perceive their ability to help their child manage distress as *improved* immediately following the completion of the active SSI (ORR+Project BRAVE), compared to an information-only control (ORR+delayed SSI).
3. Evaluate the SSI's acceptability, per self-report ratings.
4. To assess whether parents' distress tolerance improves in the active SSI (ORR+Project BRAVE) condition versus the information-only control (ORR+delayed SSI) group at two weeks follow-up.

Hypotheses associated with each of these primary aims will be as follows:

1. Parental accommodation of child anxiety will decrease significantly more among parents assigned to the ORR+Project BRAVE group, relative to parents assigned to the ORR+waitlist group from baseline to 2-week follow-up
2. Relative to parents who receive ORR, parents who receive Project BRAVE will be more likely to perceive increases in their preparedness to cope with their child's distress from before to after completing their baseline session.
3. Participants assigned to the Intervention Group will find Project BRAVE to be acceptable, indicated by a mean score of > 3 (out of 5) across Program Feedback Scale items (completed by parents assigned to the intervention group at immediate post-intervention).
4. Parents' self-reported distress tolerance will decrease significantly more among parents in the ORR+Project BRAVE group relative to those ORR+waitlist group from baseline to 2-week follow-up

Sample Size Justification

Using G*Power 3.1, sample sizes needed to detect group differences in the primary outcome (changes in accommodation from baseline to follow-up) between the BRAVE group and the Control group of small (.2), medium (.5), and large effects (.8) based on an F test, linear multiple

regression with $\alpha = .05$ and power = 0.80 were 395, 55, and 25, respectively for the primary outcome (hypothesis 1). The target sample of 300 (150 per SSI condition accounting for attrition) reflects power to detect a small to medium effect as observed by previous SSI trials.

Analytic Plan

To address *hypothesis 1*, a multiple linear regression with intervention condition (1=ORR+Project Brave; 0=ORR+waitlist control) and baseline accommodation levels (sum score of the first 9 items of the Family accommodation scale with higher scores indicating higher levels of accommodation) as predictor variables will indicate whether ORR+Project BRAVE, versus ORR+delayed SSI access, led to differential reductions in accommodation behavior from baseline to 2-week follow up. A p-value of $<.05$ will indicate a significant change in parental accommodation from baseline to 2-week follow up.

To address *hypothesis 2*, we will use the two-sample t-test to determine whether the difference between the ORR+project BRAVE and ORR+delayed SSI access group's mean ratings of the perceived post intervention condition change item is significant. A p-value of $<.05$ will indicate a significant difference between the two conditions. Descriptive statistics of the scores for both conditions will be reported as well with a mean rating above 3 (out of 5) indicating an overall, subjectively-detectable pre-to-post change.

To address *hypothesis 3*, we will examine mean scores on the Program Feedback Scale from the intervention group only. A score above 3 on any given program feedback scale item will reflect endorsement of that item (e.g. positive feedback/adequate acceptability). Thus, a mean score of 3 or higher (out of 5) across participants in this study will indicate participants found the intervention acceptable.

To address *hypothesis 4*, a multiple linear regression with intervention condition (1=ORR+Project Brave; 0= ORR+waitlist control) and baseline parental distress in the context of child negative affect as predictor variables will indicate whether ORR+Project BRAVE versus ORR+delayed SSI led to greater reductions in parental distress from baseline to 2-week follow up. Parental distress will be indicated by the sum score of the distress tolerance scale. A p-value of $<.05$ will indicate a significant change in parental distress in the context of child negative affect from baseline to 2-week follow up.

Testing Assumptions

To justify the use of linear regression models for the purpose of prediction, we will check the following principle assumptions: 1) linearity and additivity of the relationship between dependent and independent variables, 2) statistical independence of the errors, 3) homoscedasticity of the errors, 4) normality of the error distribution. Nonlinearity will be tested by checking for a symmetric distribution of points on a plot of observed versus predictive values or residual versus predicted values. To check statistical independence of the errors, residual autocorrelations will be plotted to identify values that fall outside the 95% confidence band around zero. Homoscedasticity will be checked by plotting the residuals versus the predicted

values to examine the distribution of residual scores. Finally, normally distributed errors will be checked via normal probability plot to measure skewness and kurtosis.

Missing Data

We will impute any missing data using the expectation-maximization and bootstrapping algorithm implemented with Amelia II in R after running a sensitivity analysis to ensure that data is not missing at random. These imputed datasets allow for more conservative intent-to-treat analyses than listwise deletion or last-observation carried forward. We plan to impute as many datasets as there are percent of missing data for an outcome – rounding up to the next highest percentage (e.g., If 2.4% of data is missing on an outcome, we will create 3 imputed datasets). This process will allow us to retain high power even in the presence of missing data. Cohen's d effect sizes and 95% confidence intervals for analyses will be calculated using t -values for the treatment effects obtained from the analyses with the MOTE package in R.

False Discovery Rate

The false discovery rate (FDR) will be applied to identify potential false-positive results. Q -values will be computed for p -values from each mixed effects linear model using an online calculator applying Benjamini and Hochberg's approach Benjamini and Hochberg's approach (1995); www.sdmproject.com/utilities/?show=FDR). Results from tests described above will be considered significant if FDR corrected $q < 0.05$.

Methodological Details Not Mentioned Elsewhere

Follow-up Period

We are intending on a 2 week follow-up period from the SSI but will allow up to 5 weeks post-intervention. Participants will be reminded once every two days for 6 days (total of 3 reminders) to complete the post-intervention questionnaires.

Operational Definition of Completion Rates for participants assigned to both conditions

Intervention completion rates for the ORR+ Project BRAVE group will be treated as a categorical (full completers, psychoeducational content completers, personalized-plan completers).

Categorical definitions of completion rates are defined as follows: full completers are all participants who reached the end of the SSI content (slide Q254), psychoeducational completers are all participants who received all of the psychoeducational content of the program (slide Q235), and personalized-plan completers are all participants who completed the step-by-step action plan for responding in a helpful way to their child's anxiety or avoidance (slide Q243)

Excluding Participants From Analysis

Participants will be excluded from analyses *only* if it is apparent from their free responses during the SSI that they are non-english speakers. If a participant completes either the baseline or

follow-up survey more than once, their *more-complete* response will be used in analysis (if responses are equally-complete, their *first* response will be used).

Differential Dropout Rates

We will assess for differential follow-up rates among full completers in each group by using Z-tests of differential proportions where we compare the proportion of people who drop out before completing the follow-up (Y or N) as a function of treatment condition (1 = ORR+Project Brave; 0 = waitlist control).

For participants assigned to the ORR+ delayed SSI access group, a participant must have made it through all baseline measures (i.e., they must reach the final “page” of the baseline questionnaires, or the RCADS, though it is acceptable for the participant to leave the answer blank after seeing it) to be considered a “full completer”. For participants assigned to the ORR+Project BRAVE group, a participant must have made it through all of the intervention (i.e. they must reach the final “page” of the intervention) to be considered a full completer.

To be considered a follow-up “completer”, a participant must have made it through all of the questionnaires in the follow-up surveys (i.e. they must reach the final “page” of the follow-up questionnaires though it is acceptable for the participant to leave the answer blank after seeing it).

If the p value is greater than .05 we will assume dropout was not dependent on condition assignment and can proceed with interpreting the effects of intervention assignment. If the p value for this test is less than .05 we will conclude that dropout was dependent on condition assignment, and we will take the following steps to improve the interpretability of our results. Unequal dropout between treatment groups can introduce bias in trial results; however, this is not always the case (Bell, Kenward, Fairclough, & Horton, 2013; <https://doi.org/10.1136/bmj.e8668>). One major concern is that, if data is not missing at random, systematic differences may exist between “dropouts” and “completers” that cannot be corrected for, limiting the interpretability of our results. For example, if more control condition participants experienced a worsening of clinical symptoms and dropped out before completing follow-up measures, this worsening of symptoms would not be captured by completers’ data (or by data imputed based on the available completers’ data). Thus, should unequal dropout exist between conditions in the present study, we will report the results of our main analyses while highlighting (1) limitations to interpretation, and (2) ways in which this will inform future intervention development.

Further, if unequal dropout is present, we will run a sensitivity analysis to determine a range of possible effect sizes for our outcomes of interest, varying how much “dropout participants” may have changed on each outcome. To establish lower- and upper-end estimates of effect size, we will: (1) calculate residual change for each of our 3 outcomes, (2) identify the 25th and 75th percentile values for residual change in each outcome, (3) run analyses for each outcome where we impute the lower residual change value (25th percentile) for all dropouts/missing data, as well as the higher residual change value (75th percentile) for all dropouts/missing data. This approach explicitly assumes data are not missing at random, providing a more unbiased estimate of the overall treatment effect in the presence of unequal dropout.

Exploratory Moderation Tests

We will also conduct exploratory moderation tests examining various baseline variables as moderators of the SSI's impact on outcome, using the same approaches to missing data and corrections for multiple tests as described elsewhere in the pre-registration

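### The sample sizes 395, 55 and 25 belong to f² = .02, .15 and .35, not to the stated effects of .2, .5 and .8; read as Cohen's d, those effects need about twice as many parents.

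*SAP*

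**What the plan says.** The SAP's Sample Size Justification reports G*Power 3.1 totals for the primary outcome, the group difference in accommodation. The inputs are "small (.2), medium (.5), and large effects (.8) based on an F test, linear multiple" regression at alpha .05. The result is that sizes at "power = 0.80 were 395, 55, and 25, respectively for the primary outcome (hypothesis 1". The paragraph does not name the metric of .2, .5 and .8.

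It then concludes: "The target sample of 300 (150 per SSI condition accounting for attrition) reflects power to detect a small to medium effect", with reference to previous single-session trials.

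Two other places bear on the reading:

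- The Analytic Plan specifies for hypothesis 1 "a multiple linear regression with intervention condition (1=ORR+Project Brave; 0=ORR+waitlist control) and baseline accommodation levels" as predictors. The model therefore has two predictors, of which one is tested.
- Under Missing Data, the plan states its reporting metric: "Cohen's d effect sizes and 95% confidence intervals for analyses will be calculated using t -values" for the treatment effects.

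**The concern.** The values .2, .5 and .8, labelled small, medium and large for a difference between two groups, are the usual benchmarks for Cohen's d. A regression F test takes f² as its input, and the usual f² benchmarks are .02, .15 and .35. The three sample sizes looked as if they came from the second set and had been printed beside the first.

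This is the SAP's only power statement for the primary outcome. A reader who takes it at face value will believe that d = .5 needs 55 parents and d = .2 needs 395, and that 300 parents fall only somewhat short of 80% power for d = .2. Because the trial will report Cohen's d, observed effects will be compared directly with these figures.

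**Working it through.** **Inputs.** From the SAP: alpha .05, power .80, F test in linear multiple regression, stated totals 395/55/25, target 300 with 150 per arm (Sample Size Justification); two predictors, one tested (Analytic Plan, hypothesis 1). The SAP gives neither a baseline-to-follow-up correlation nor an attrition rate, so both are varied below as assumptions.

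**Method.** Power is the upper tail of a noncentral F distribution with 1 and N − k − 1 degrees of freedom (k predictors in the model) and noncentrality λ = f²N. The required N is the smallest that gives power of at least .80.

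**Step 1: reproduce the stated figures.** With f² = .02, .15 and .35, N comes out as 395, 55 and 25 exactly, whether the model has one, two or three predictors. The noncentralities are .02 × 395 = 7.90, .15 × 55 = 8.25 and .35 × 25 = 8.75.

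**Step 2: try the stated effects.** With equal arms the treatment indicator has variance 1/4, so f² = d²/4. For d = .2, .5 and .8 this gives f² = .01, .0625 and .16. The table uses one tested predictor of two.

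| Reading of .2 / .5 / .8 | Required total N |
|---|---|
| d (f² = d²/4) | 787 / 128 / 52 |
| d, one-sided | 620 / 101 / 41 |
| f (f² = .04/.25/.64) | 199 / 34 / 15 |
| f² | 42 / 18 / 13 |
| correlation r | 191 / 26 / 8 |
| R² | 34 / 11 / 6 |
| **SAP** | **395 / 55 / 25** |

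No row matches. As a cross-check on the d row, the normal approximation for two means gives 786/126/50.

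**Step 3: size of the gap, reading the effects as d.** The ratios are 787/395 = 1.99, 128/55 = 2.33 and 52/25 = 2.08. At the stated totals the noncentralities are only .01 × 395 = 3.95, .0625 × 55 = 3.44 and .16 × 25 = 4.00. Power is then .51, .44 and .48.

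**Step 4: what the stated totals do detect.** Inverting the conversion, d = 2√f²: 2√.02 = .28, 2√.15 = .77 and 2√.35 = 1.18.

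**Step 5: could baseline adjustment explain the figures?** If d is in raw SD units and baseline correlates ρ with follow-up, then f² = d²/[4(1 − ρ²)].

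| ρ (assumed) | N for d = .2 / .5 / .8 |
|---|---|
| 0 | 787 / 128 / 52 |
| .5 | 591 / 97 / 39 |
| .7 | 403 / 67 / 28 |
| .75 | 346 / 57 / 24 |
| .8 | 285 / 48 / 20 |

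No common ρ tried yields all three figures. An unadjusted change-score comparison does not either: at ρ = .75 it gives 394/64/26.

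**Step 6: what 300 supports.** d is in units of the SD left after baseline adjustment; the attrition rates are assumptions.

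| Analysed N | d at 80% power | Power for d = .2 | Power for d = .5 |
|---|---|---|---|
| 300 (no loss) | .325 | .41 | .99 |
| 240 (20% loss) | .36 | .34 | .97 |
| 210 (30% loss) | .39 | .30 | .95 |

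**The case against.** The mismatch itself is hard to dispute; the case on the other side concerns how much it matters.

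- **None of the three totals sets the trial size.** The target of 300 is supported by effects seen in earlier trials, and the claim of power for a small-to-medium effect stays true after correction: d = .325 to .39 lies between .2 and .5. This stands. No test, decision rule or recruitment target changes.
- **The two-fold figure depends on the reading.** The SAP names no metric. Taken literally as f², the stated totals would be too large, and with d in raw SD units a strong baseline correlation nearly closes the gap for the small effect (403 against 395 at ρ = .7). This stands as a condition on the size of the error. It does not remove the error, because none of these readings yields the three totals together.
- **The totals may be right for the words small, medium and large in the f² metric, with only the bracketed numbers mistyped.** This is quite possible, and relabelling is one of the two remedies below. The printed statement is still wrong as it reads.
- **The SAP already shows that a small effect needs more than its 300, and it plans confidence intervals.** Both are true and limit the harm. Even so, 395 against 300 suggests a modest shortfall, whereas 787 against 300 is a large one.
- **The attrition rate may be in the protocol.** That is fair, so its absence here is not counted as an error.

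**Conclusion.** The concern holds. The totals 395, 55 and 25 are those for f² = .02, .15 and .35, and they do not correspond to effects of .2, .5 and .8 on any reading tried. Read as Cohen's d in residual SD units, which the labels and the plan's reporting metric support, the required totals are understated by a factor of 2.0 to 2.3, and power at the stated totals is 44% to 51% instead of 80%. The size and direction depend on that reading; the mismatch does not. The target of 300 is not overturned. What changes is its stated sensitivity: 80% power at d = .325 if all 300 are analysed, and 41% power for d = .2, with less after attrition. It is a definite numerical error in the primary power statement, with limited consequences for the design.

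**What to change.** Keep the target of 300 and correct the Sample Size Justification:

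1. Name the effect metric and, if it is d, say that it is in units of the SD remaining after adjustment for baseline.
2. Either label the totals 395/55/25 as f² = .02/.15/.35 (d = .28/.77/1.18 with equal arms), or give 787/128/52 for d = .2/.5/.8.
3. Replace the closing sentence with one that ties power to the number analysed, for example: *With 300 parents analysed the trial has 80% power for d = .325; with an expected X% attrition (for instance 20%, 240 analysed) for d = .36.* The sponsor should supply X.
4. If the sponsor wants credit for baseline adjustment on the raw SD scale, state the assumed correlation and its source.

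The cost is wording only. No additional parents are needed and the analysis is unchanged; the stated sensitivity becomes less favourable.

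### Hypothesis 2's descriptive rule reads any condition mean above 3 as a perceived change, with no allowance for sampling error (minor)

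*SAP*

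**What the plan says.** In the SAP's Analytic Plan, the paragraph on hypothesis 2 does two things.

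- **The test.** The plan states that "we will use the two-sample t-test to determine whether the difference between the ORR+project BRAVE and ORR+delayed SSI access group's mean ratings" on the perceived-change item is significant, and that a p-value below .05 "will indicate a significant difference between the two conditions". Under False Discovery Rate, results of the tests also have to meet a q-value criterion of 0.05.
- **The descriptive reading.** The paragraph then adds: "Descriptive statistics of the scores for both conditions will be reported as well". It fixes how those statistics are to be read, namely a "mean rating above 3 (out of 5) indicating an overall, subjectively-detectable pre-to-post change".

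Under Study Aims and Hypotheses, hypothesis 2 is comparative: "Relative to parents who receive ORR, parents who receive Project BRAVE will be more likely to perceive increases in their preparedness" when faced with the child's distress. Aim 2 begins "To assess whether parents' perceive their ability to help their child manage distress as *improved* immediately following the completion of the active SSI", and its sentence goes on to name the information-only control as the comparator.

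The SAP gives no response anchors, no SD and no error rate for this item. The planned size is 150 per condition (Sample Size Justification).

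**The concern.** The second sentence goes beyond listing means. It fixes in advance what a mean above 3 will be taken to show, and the only input is one condition's sample mean. No standard error, interval or minimum excess is attached, so 3.01 receives the same label as 3.60.

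The SAP's other safeguards do not reach this statement. The false discovery rate step works on p-values, and a comparison of a mean with 3 produces none. The 95% confidence intervals promised under Missing Data belong to effect sizes derived from the t-values for treatment effects, not to condition means. The t-test shows whether the conditions differ. It does not show whether either condition's mean lies above 3.

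What is at stake is the wording of a secondary statement. A condition mean that exceeds 3 only by chance could be reported, under a pre-registered rule, as a change that parents noticed.

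**Working it through.** The SAP states no error rate for this rule, so there is no figure of its own to reproduce.

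**Inputs from the SAP**
- Cut-off: mean above 3 on an item scored out of 5, applied to both conditions (Analytic Plan).
- Planned n: 150 per condition (Sample Size Justification). The number analysed for this item is not given, so n = 50 to 150 is shown.

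**Assumptions**
- Ratings are integers from 1 to 5, parents are independent, and 3 is the no-change point, as the cut-off suggests.
- The SD is not given; 0.5 to 1.41 is used (1.41 is a uniform spread over the five scores).
- The true mean is exactly 3 unless stated otherwise.

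**Step 1: one condition.** The exact distribution of the sum of n ratings comes from convolution. For a symmetric distribution about 3, p = P(mean > 3) = (1 − P(mean = 3))/2. At SD 1.0 and n = 150, P(mean = 3) = 0.0326, so p = (1 − 0.0326)/2 = 0.4837.

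**Step 2: at least one of two conditions.** 1 − (1 − p)² = 1 − 0.5163² = 0.733. Both conditions: 0.4837² = 0.234.

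| SD | p per condition, n = 150 | At least one, n = 150 | At least one, n = 50 |
|---|---|---|---|
| 0.5 | 0.467 | 0.716 | 0.690 |
| 0.71 | 0.477 | 0.727 | 0.709 |
| 1.0 | 0.484 | 0.733 | 0.721 |
| 1.1 | 0.485 | 0.735 | 0.724 |
| 1.41 | 0.489 | 0.738 | 0.730 |

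The unknown SD and n hardly matter. A simulation of 20,000 trials at SD 1.0 and n = 150 gave 0.730 for at least one condition.

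**Step 3: dependence on the true mean.** At SD 1.0 and n = 150 the standard error is 1/√150 = 0.0816. By the normal approximation:
- true mean 2.9: 0.110 per condition; at least one, 1 − 0.890² = 0.21;
- true mean 3.1: 0.890 per condition; at least one, 1 − 0.110² = 0.99.

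**Step 4: the test that decides hypothesis 2.** In the same simulated trials, with both true means at 3, the t-test gave p < .05 in 4.9%. A significant result favouring BRAVE together with a BRAVE mean above 3 occurred in 2.4%.

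**Step 5: requiring the lower 95% limit to exceed 3.** The nominal chance is 2.5% per condition. For either condition it is 1 − 0.975² = 0.049. Simulated per-condition rates, with ratings spread 10/20/40/20/10%, were 0.024 at n = 150 and 0.026 at n = 110. At n = 150 the mean must exceed 3 + 1.976 × SD/√150, which is 3.08 (SD 0.5), 3.16 (SD 1.0) or 3.23 (SD 1.41).

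**The case against.** The strongest reply is that the sentence is descriptive and the plan never asks it to decide anything. Hypothesis 2 compares BRAVE with ORR, aim 2 names the control condition, and the t-test answers both. That stands, and it limits the point in four ways.

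- **A reader might infer that hypothesis 2 has a false-positive rate of about 73%.** The documents do not support this. That figure belongs to the descriptive label and counts a hit in either condition, control included. For BRAVE alone it is about 48%, and the t-test keeps its error near 5%.
- **The figures are sensitive to the true mean.** Any bare threshold is crossed about half the time when the truth lies on it. The SAP gives no anchors to confirm that 3 means no change, and a shift of 0.1 either way alters the rate greatly (Step 3).
- **A reader might infer that labelling both conditions, with no difference between them, is a false claim.** It is not. If both true means were 3.2 and 3 meant no change, parents in both conditions would on average perceive a change. The label speaks of pre-to-post change, not of a BRAVE effect. Nothing in the SAP tells the analyst to use it as evidence for BRAVE.
- **The word detectable is qualified as subjective.** It refers to what the parent notices, so it is not a claim of statistical detection.

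What the reply does not remove is that a conclusion about a group's average is still tied in advance to a point estimate without its uncertainty.

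**Conclusion.** The point holds as a minor weakness in a secondary descriptive statement. If the item runs 1 to 5, 3 means no change and the true mean is exactly 3, the rule labels a given condition as changed about 47–49% of the time at 150 per condition. It labels at least one of the two in about 69–74% of trials over n = 50 to 150 and SD 0.5 to 1.41. These rates describe the label only. The between-condition decision on hypothesis 2, its error rate and the treatment-effect estimate are unaffected, and the SAP does not treat the label as evidence for BRAVE.

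**What to change.** In the Analytic Plan, replace the descriptive sentence for hypothesis 2 with wording such as: *Each condition's mean rating will be reported with its 95% confidence interval. A perceived pre-to-post change will be stated for a condition only if the lower limit exceeds 3. This is a within-condition description; evidence for a BRAVE effect rests on the between-condition test alone.*

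The last clause only makes explicit what the plan already implies.

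The cost is one sentence and two confidence intervals, with no new data and no change to the t-test. The downside is that a mean slightly above 3 no longer counts as a change: at 150 per condition and an SD of 1.0, it would have to exceed about 3.16.

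### The acceptability verdict for hypothesis 3 has an inconsistent threshold and unit and, separately, rests on a bare sample mean with no allowance for sampling error

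*SAP*

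**What the plan says.** Acceptability is the third of four aims under Study Aims and Hypotheses in the SAP. Hypothesis 3 there states that parents will find the program acceptable, "indicated by a mean score of > 3 (out of 5) across Program Feedback Scale items".

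The Analytic Plan then describes the analysis: "we will examine mean scores on the Program Feedback Scale from the intervention group only". It sets an item rule, "A score above 3 on any given program feedback scale item will reflect endorsement of that item", and presents the overall verdict as following from it: "a mean score of 3 or higher (out of 5) across participants in this study will indicate participants found the intervention acceptable".

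No test, significance level, standard error or confidence limit is attached to this verdict. The intervals planned under Missing Data are tied to comparisons between arms: "95% confidence intervals for analyses will be calculated using t -values for the treatment effects obtained from the analyses". The False Discovery Rate section works on p-values from models, and hypothesis 3 produces none.

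**The concern.** Two things look wrong, and they are independent of each other.

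First, the criterion is not stated in one way. A mean of exactly 3 fails in the hypothesis and passes in the Analytic Plan. The looser version does not follow from the item rule it is drawn from, since a score of 3 is not endorsement under that rule. The unit shifts as well: across items in the hypothesis, any single item in the item rule, and across participants in the verdict. A scale mean can exceed 3 while one item's mean lies below it, so whether each item or only the scale mean has to pass can affect the conclusion.

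Second, under either threshold, an observed mean barely above 3 counts as success however imprecise it is. The SAP would report that parents found the program acceptable even if the data were fully compatible with a true mean below 3.

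**Working it through.** The SAP gives no error rate, power or sample size for hypothesis 3, so there is no figure of its own to reproduce.

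**Inputs**
- Cut-off: 3 out of 5 (SAP, both places).
- Number of raters: not stated. The Sample Size Justification plans "150 per SSI condition accounting for attrition". I assume 100 to 150 raters, with 75 as a low case.
- SD of the per-parent score: not stated. I assume 0.7 to 1.0.

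**The bare-mean rule**

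SE = SD/√n. The smallest value is 0.7/√150 = 0.057 and the largest is 1.0/√100 = 0.10. The probability of declaring acceptability at true mean μ is 1 − Φ((3 − μ)/SE).

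| True mean | SE 0.057 | SE 0.10 |
|---|---|---|
| 3.00 | 1 − Φ(0) = 50% | 1 − Φ(0) = 50% |
| 2.95 | 1 − Φ(0.875) = 19% | 1 − Φ(0.5) = 31% |
| 2.90 | 1 − Φ(1.75) = 4% | 1 − Φ(1.0) = 16% |

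Under the normal approximation, the 50% at a true mean of 3 does not depend on the SD or on n.

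**How much the choice of threshold matters**

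I took a single item scored 1 to 5 with true mean 3, under four assumed response distributions (SD 0.89 to 1.41), and computed the distribution of the sample mean exactly. At n = 150, a mean strictly above 3 occurs 48% to 49% of the time, and a mean of 3 or more 51% to 52%. The two thresholds disagree only when the sample mean is exactly 3. That has probability 2.3% to 3.6% at n = 150, and about 3% to 5% at n = 75. It was not computed for an average over several items.

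**The lower-limit rule**

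If the lower limit of the two-sided 95% interval must exceed 3, the probability of acceptance at a true mean of 3 is 2.5%. The observed mean must exceed 3 + t(0.975, n − 1) × SD/√n:
- n = 150, SD 0.75: 3.12
- n = 150, SD 1.0: 3.16
- n = 100, SD 1.0: 3.20

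Power at a true mean of 3.25 (noncentral t):
- n = 150, SD 0.75: 98%
- n = 150, SD 1.0: 86%
- n = 100, SD 1.0: 70%

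At a true mean of 4 with SE 0.10, the expected result is (4 − 3)/0.10 = 10 standard errors above the cut-off, so both rules give the same verdict.

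**The case against.** The strongest reply is that hypothesis 3 is a one-arm benchmark and not a test. The Sample Size Justification names change in accommodation as the primary outcome and sizes the trial on that alone. Where the plan intends inference, in hypotheses 1, 2 and 4, it gives a p-value criterion; here it says only that means will be examined. Any cut-off on a point estimate passes about half the time when the truth sits on it, so the 50% shows that no margin was set. It does not show how likely a wrong verdict is in this trial. Nothing in the SAP suggests that ratings near 3 are expected. Reporting the mean with its interval, without a new pass/fail rule, would meet much of the concern.

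Most of this stands, and it limits the weight of the point. It does not remove it, because the plan draws a yes/no conclusion from the mean and states the boundary in two ways.

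Two stronger readings should be resisted. A reader might infer that the conflicting thresholds cause the 50%. They do not: they shift it by a few percentage points at most, and the rest comes from having no uncertainty margin. A reader might also extend the criticism to hypothesis 2, where the plan speaks of "a mean rating above 3 (out of 5) indicating an overall, subjectively-detectable pre-to-post change". That sentence is introduced as descriptive, and a two-sample t-test decides that hypothesis, so the extension is not supported.

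**Conclusion.** The point holds and is minor. The threshold and unit for hypothesis 3 are inconsistent, which is a matter of wording except that the plan leaves open whether each item or the scale mean must pass. Independently, the verdict has no allowance for sampling error. At a true mean of 3 it declares acceptability about half the time; at 2.95, 19% to 31%; at 2.90, 4% to 16%. The last two ranges rest on an assumed SD of 0.7 to 1.0 and 100 to 150 raters; the first does not.

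The weakness matters only if true ratings lie within about 0.2 of 3. The SAP does not support a claim that the trial's main conclusion is at risk, since acceptability is one of several listed aims and not the outcome on which the trial is sized. Nor does it call a score of 3 neutral; it says only that endorsement begins above 3.

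**What to change.** Use one rule under both Study Aims and Hypotheses and Analytic Plan: the intervention is acceptable if the lower limit of the two-sided 95% confidence interval for the mean Program Feedback Scale score, items averaged per parent, is above 3. State that individual item means will be reported with intervals as description and do not decide the verdict. Leave the descriptive sentence under hypothesis 2 as it is.

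The change costs an edit in two places and one confidence interval, with no added data or sample. The downside is a slightly stricter criterion: at n = 150 and an SD of 0.75 to 1.0, the observed mean must exceed about 3.12 to 3.16. A program whose true mean is only modestly above 3 could miss it, more so if few parents complete the scale.
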